6.3.2.3 Overall Summary of Primary and Secondary Endpoints in Hierarchical Testing

The overall summary table of treatment comparisons of all primary and secondary endpoints tested hierarchically displays the following statistics:

- Continuous endpoints involving change from OP or baseline
 - n (i.e., number of subjects in the analysis set), overall LSM change and 95% CI for each treatment group
 - Difference in overall LSM changes between treatment groups (rimegepant placebo), 95% CI, and p-value.

This applies to the primary endpoint and the following secondary efficacy and outcomes endpoints: mean change in the number of migraine days per month in the overall DBT Phase (see main analysis in Section 6.3.1.1); mean change in the number of migraine days per month in the first month of the DBT Phase (see main analysis in Section 6.3.1.1); MSQoL restrictive role domain score change from baseline at Week 12 (see Section 6.5.1); MIDAS total score change from baseline at Week 12 (see Section 6.5.2); and EQ-5D-5L VAS score change from baseline at Week 12 (see Section 6.5.3).

• Continuous endpoints not involving change from OP or baseline

- $\circ~$ n, overall LSM and 95% CI for each treatment group
- Difference in overall LSMs between treatment groups (rimegepant placebo), 95% CI, and p-value.

This applies to the secondary efficacy endpoint of the mean number of acute migraine-specific medication days per month in the last month of the DBT Phase (see Section 6.3.2.2).

- Binary endpoints
 - Response rate ("n/N") and 95% CI for each treatment group
 - Stratified percentage difference between treatment groups (rimegepant placebo), 95% CI, and p-value.

This applies to the secondary efficacy endpoint of the percentage of subjects with $\geq 50\%$ reduction in the mean number of moderate or severe migraine days per month in the last month of the DBT Phase (see Section 6.3.2.1).

Endpoints are displayed in the order presented in Sections 3.2.1 and 3.2.2. P-values that are determined to be significant based on the testing hierarchy are flagged.

If the primary endpoint is significant, then the secondary efficacy and outcomes research endpoints are tested hierarchically, each at a 2-sided alpha level of 0.05, in the order specified in Section 3.2.2. Thus, a secondary efficacy or outcomes research endpoint is tested only if the preceding secondary endpoint in the hierarchy is determined to be significant (i.e., p-value \leq 0.05). If a test in the hierarchy is not significant, then any further tests on endpoints in the sequence have p-values presented only for descriptive purposes, and no conclusions are drawn from those results.

For a given treatment comparison of a continuous endpoint, the null hypothesis of interest H₀ is that the mean change observed on rimegepant (denoted $\mu_{rimegepant}$) is equal to the one observed on placebo (denoted $\mu_{placebo}$), i.e., H₀: $\mu_{rimegepant} = \mu_{placebo}$. The alternative 2-sided hypothesis of interest H₁ is that the mean changes observed on rimegepant and placebo differ, i.e., H₁: $\mu_{rimegepant} \neq \mu_{placebo}$. For a given treatment comparison of a binary endpoint, the hypotheses are based on percentages instead of mean changes.

6.3.3 Exploratory Efficacy Endpoints

For exploratory efficacy endpoints, no attempt is made to adjust for multiplicity. Any exploratory endpoints for which p-values are produced are evaluated at an unadjusted, 2-sided alpha level of 0.05 and presented only for descriptive purposes.

This section also includes analyses of endpoints based on headache days that are typically included for migraine prevention studies. These are not formally prespecified in Section 3.2.3.

6.3.3.1 Reduction in Number of Headache Days per Month in the DBT Phase

The number of headache days per month is prorated to 28 days and defined analogously to

migraine days per month (see Section 6.3.1).

A headache day is defined in Section 9.2.6.

Analyses are analogous to those described in Sections 6.3.1.1 and 6.3.1.2 for the reduction in migraine days per month during the DBT and OLE Phases, respectively.

In the percent change analyses, subjects must also have ≥ 1 headache day (absolute not prorated) of appropriate pain intensity in the OP analysis period to be included.

Reduction in Headache Days per Month in the DBT Phase

Analyses are based on the DBT migraine analysis set with eDiary efficacy dates in the OP and on-DBT efficacy analysis periods.

Descriptive Analyses

The table of values and changes (both absolute and percent) from the OP in the number of headache days per month in the DBT Phase is provided, and has the same format as the one described in Section 6.3.1.1.

Treatment Group Comparisons

Treatment groups are compared using a linear mixed effects model with repeated measures with the same attributes as the one for the primary endpoint except that change from the OP in number of total headache days per month is the dependent variable. The table has the same format as the one described in Section 6.3.1.1.

These analyses are repeated for moderate or severe headache pain intensity. All variables in the model are the same, except change from the OP in number of moderate or severe headache days per month is the dependent variable. The table has the same format.

Reduction in Headache Days per Month in the OLE Phase

Analyses are based on the OL rimegepant migraine analysis set with eDiary efficacy dates in the OP and on-OL rimegepant efficacy analysis periods.

The table of values and changes (both absolute and percent) from the OP in the number of headache days per month in the OLE Phase is provided, and has the same format as the one described in Section 6.3.1.2.

6.3.3.2 Percentages of Subjects with Reduction in Number of Headache Days per Month in the DBT Phase

The percentages of subjects with reduction in the number of headache days during the DBT and OLE Phases are defined and assessed analogously to the percentages of subjects with reduction in the number of migraine days during the DBT and OLE Phases (see in Section 6.3.2.1).

Percentages of Subjects with Reduction in Headache Days per Month in the DBT Phase

Analyses are based on the DBT migraine analysis set with eDiary efficacy dates in the OP and on-DBT efficacy analysis periods.

For each pain intensity and select percentage reduction, the percentages of subjects with reductions from the OP in the number of headache days per month in the DBT Phase are compared between treatment groups using Mantel-Haenszel risk estimation with stratification by randomization stratum (yes, no). The table has the same format as the one described in Section 6.3.2.1.

Percentages of Subjects with Reduction Headache Days per Month in the OLE Phase

Analyses are based on the OL rimegepant migraine analysis set with eDiary efficacy dates in the OP and on-OL rimegepant efficacy analysis periods.

The frequency table of reductions from the OP in the number of headache days per month in the OLE Phase is provided, and has the same format as the one described in Section 6.3.2.1.

6.3.3.3 Reduction in the Number of Migraine Days per Week and Headache Days per Week in the First Month of the DBT Phase

The number of migraine days per week in the first month (Weeks 1 to 4) of the DBT Phase is examined relative to the number of migraine days per week in the OP for the DBT first month migraine analysis set, i.e., subjects in the DBT efficacy analysis set with \geq 24 days of eDiary efficacy data (not necessarily consecutive) in both the OP analysis period and first month of the on-DBT efficacy analysis period.

Weeks 1 to 4 of the DBT Phase are defined as follows:

- Week 1: study days 1 to 7
- Week 2: study days 8 to 14
- Week 3: study days 15 to 21
- Week 4: study days 22 to 28.

See Sections 7.2 and 7.3 for the definition of analysis periods and study days used to define analysis visit windows.

Analyses are based on the DBT first month migraine analysis set using eDiary efficacy dates in the OP and on-DBT efficacy analysis periods.

The number of migraine days per week is prorated to 7 days and derived as follows:

- OP: 7 × (total number of migraine days in the OP analysis period)/(total number of eDiary efficacy data days in the OP analysis period)
- Week (7-day interval) of the on-DBT efficacy analysis period: 7 × (total number of migraine days in the week)/(total number of eDiary efficacy data days in the week).

The number of headache days per week is derived analogously.

Descriptive Analyses

The table of values and changes (both absolute and percent) from the OP in the number of migraine days per week in the first month (Weeks 1 to 4) of the DBT Phase is provided, and summarizes parameters descriptively as continuous variables (including 2-sided normal 95% CIs for mean change) by treatment group and pain intensity (total; moderate or severe). In the percent change analyses, subjects must also have ≥ 1 migraine day of appropriate intensity (absolute not prorated) in the OP analysis period to be included.

Treatment Group Comparisons

Treatment groups are compared using a linear mixed effects model with repeated measures and the following attributes:

- Variables: change from the OP in number of total migraine days per week as the dependent variable; number of total migraine days per week in the OP as a covariate; treatment group, randomization stratum, week (i.e., Weeks 1 to 4 of the DBT Phase), and the week-by-treatment group interaction as fixed effects.
- Covariance structure for repeated measures accounting for within-subject correlated errors: See Section 6.3.1.1.
- SE estimation method: See Section 6.3.1.1.

The table displays the following model estimates:

- LSM change from OP, SE, and 95% CI by week for each treatment group
- Difference in LSM changes from OP between treatment groups (rimegepant placebo), SE, 95% CI, and p-value for each week.

See Section 9.3.1 for example SAS code. Model estimates by randomization stratum (yes, no) are presented in the same table, using additional linear mixed effects models that exclude randomization stratum as a fixed effect.

These analyses are repeated for moderate or severe pain intensity. All variables in the model are the same, except (1) change from the OP in number of moderate or severe migraine days per week is the dependent variable, and (2) number of moderate or severe migraine days per week in the OP is the covariate. The corresponding table has the same format.

Results support exploratory objective #3.

All analyses described above are performed analogously for headache days per week.

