- Included in the DBT migraine analysis set: ≥ 14 days of eDiary efficacy data (not necessarily consecutive) in both the OP and ≥ 1 month (i.e., 4-week interval) of the DBT Phase
 - Month 1: \leq 4 weeks *
 - Month 2: > 4 to ≤ 8 weeks *
 - Month 3: > 8 to ≤ 12 weeks *
- Excluded from the DBT migraine analysis set
 - \circ < 14 days of eDiary efficacy data in the OP
 - < 14 days of eDiary efficacy data in all 3 months of the DBT Phase.

In the categories marked with "*", subjects must have ≥ 14 days of efficacy data (not necessarily consecutive) in the specified month to be evaluable.

Descriptive Analyses

The table of values and changes (both absolute and percent) from the OP in the number of migraine days per month in the DBT Phase is provided for the DBT migraine analysis set, and summarizes parameters descriptively as continuous variables (including 2-sided normal 95% CIs for mean change) by treatment group and by pain intensity in each month of the DBT Phase and overall DBT. Pain intensity categories are (1) total (mild, moderate, severe, none, or not reported) and (2) moderate or severe. The table also presents results by subgroup level for all efficacy subgroups of interest described in Section 4.3.

In the percent change analyses, subjects must also have ≥ 1 migraine day (i.e., absolute not prorated to 28 days) of appropriate migraine severity in the OP analysis period to be included.

Treatment Group Comparisons

Analyses are based on DBT migraine analysis set and total pain intensity, unless otherwise specified.

Main Analysis: DBT Migraine Analysis Set

The main analysis of the primary endpoint uses a linear mixed effects model with repeated measures and the following attributes:

- Variables: change from the OP in number of total migraine days per month as the dependent variable; number of total migraine days per month in the OP as a covariate; treatment group, randomization stratum, month (i.e., Months 1 to 3 of the DBT Phase), and the month-by-treatment group interaction as fixed effects.

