- Covariance structure for repeated measures accounting for within-subject correlated errors: assumed to be homogeneous across treatment groups and initially specified as unstructured. If the model fails to converge or cannot be fit with an unstructured covariance structure, then other covariance structures are specified in the following hierarchical order: Toeplitz (which has heterogenous variances and heterogenous correlations between elements); first-order autoregressive with heterogeneous variances; and first-order autoregressive with homogeneous variances.
- SE estimation method: Huber-White robust "sandwich" (refer to the Core SAP).

The table displays the following model estimates:

- Least-squares mean (LSM) change from OP, standard error (SE), and 95% CI by month and overall DBT for each treatment group
- Difference in LSM changes from OP between rimegepant and placebo, SE, 95% CI, and pvalue at each month and overall DBT. Results in the last month support the primary objective, results in the overall DBT support secondary objective #2, results in the first

month support secondary objective #3, and results in the second month support exploratory objective #1.

See Section 9.3.1 for example SAS code. Model estimates by randomization stratum (yes, no) are presented in the same table, using additional linear mixed effects models that exclude randomization stratum as a fixed effect.

The main analyses are repeated for moderate or severe pain intensity to support exploratory objective #1. All variables in the model are the same, except (1) change from the OP in number of moderate or severe migraine days per month is the dependent variable, and (2) number of moderate or severe migraine days per month in the OP is the covariate. The corresponding table has the same format.

The line plot displays the LSM change from OP in the number of total migraine days from OP per month on the y-axis versus month of the DBT Phase on the x-axis by treatment group. Error bars denote 95% CIs.

J2R Imputation Sensitivity Analysis: DBT Efficacy Analysis Set

A sensitivity analysis of the primary endpoint uses the same linear mixed effects model as the main analysis, but with jump to reference (J2R) to impute missing data (i.e., change from OP in the number of total migraine days per month) in Months 1 to 3 for the DBT efficacy analysis set. Placebo is considered the "reference".

The analysis is performed using the following steps:

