9.2.5 Migraine Day

A migraine day is defined as a day of eDiary efficacy data with either (1) or (2) or (3):

- 1) Qualified migraine headache, defined as meeting both criteria a and b:
 - a. Headache lasting \ge 30 minutes: "Yes" response to the question about lasting \ge 30 minutes
 - b. Meeting ≥ 1 of the following criteria (i or ii):
 - i. ≥ 2 of the following pain features:
 - 1. Unilateral: "Yes" response to the question about unilateral
 - 2. Pulsating: "Yes" response to the question about pulsating
 - 3. Moderate or severe pain intensity
 - 4. Worsen or avoid physical activity: "Yes" response to the question about worsen or avoid physical activity
 - ii. ≥ 1 of the following associated symptoms:
 - 1. Nausea: "Yes" response to the question about nausea
 - 2. Vomiting: "Yes" response to the question about vomiting

- 3. Both photophobia and phonophobia: "Yes" responses to the questions about photophobia and phonophobia
- 2) Acute migraine-specific medication day (see Section 9.2.4)
- 3) Non-scheduled OL rimegepant dosing day (see Section 9.4).

Migraine days are a subset of headache days (see Section 9.2.6).

If there are multiple sets of efficacy parameters on the same finding date, then data from all sets are used cumulatively to assess migraine day status on that day, regardless of finding time. Migraine pain intensity is set to the greatest pain intensity on that day.

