9.3 SAS Code

9.3.1 Linear Mixed Effects Model with Repeated Measures

Consider the following variables used to evaluate the primary efficacy endpoint using a linear mixed effects model with repeated measures:

- mdmchg: change from the OP in migraine days per month; continuous variable
- mdmop: migraine days per month during the OP; continuous variable
- month: month; categorical variable with levels of 1, 2, and 3
- rndstr: randomization stratum; categorical variable with levels of 1 and 2 to denote yes and no, respectively
- trt: treatment group; categorical variable with levels of 1 and 2 to denote rimegepant and placebo, respectively
- usubjid: unique subject identifier; categorical variable.

Then the SAS code is as follows:

proc mixed data = xxx empirical; class usubjid rndstr trt month; model mdmchg = mdmop rndstr trt month trt*month; repeated month / subject = usubjid type = un; /* unstructured covariance */ lsmeans trt trt*month / alpha = 0.05 cl diff; run;

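### The headache-day models in SAP 6.3.3.1, read literally, keep observation-phase migraine days as the baseline covariate; the section contradicts itself on this and some precision is probably lost

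*SAP*

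**What the plan says.** The primary model in SAP 6.3.1.1 has "number of total migraine days per month in the OP as a covariate". The example code in SAP 9.3.1 agrees: "model mdmchg = mdmop rndstr trt month trt*month", where mdmop is OP migraine days per month.

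For headache days, SAP 6.3.3.1 makes three statements:

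- A general one near the start of the section: "Analyses are analogous to those described in Sections 6.3.1.1 and 6.3.1.2".
- For total headache days, the model has the primary model's attributes, "except that change from the OP in number of total headache days per month is the dependent variable".
- For moderate or severe headache days, again only the outcome is named as changed: "All variables in the model are the same, except change from the OP in number of moderate or severe headache days".

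Elsewhere the SAP states a covariate switch outright. When 6.3.1.1 repeats the main analysis for moderate or severe pain, a second numbered exception says that "number of moderate or severe migraine days per month in the OP is the covariate". The weekly migraine-day repeat in 6.3.3.3 does the same: "number of moderate or severe migraine days per week in the OP is the covariate". The weekly headache-day analyses in 6.3.3.3 are said only to be done by analogy, with no covariate named.

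**The concern.** A change score is normally adjusted for its own baseline, because that baseline is usually the strongest single predictor of the change. The two specific sentences in 6.3.3.1 list what differs from the primary model, and the covariate is not on either list. A programmer who follows them would adjust change in headache days for OP migraine days. In the moderate or severe model the covariate would then differ from the outcome in both event type and pain intensity.

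Two things are at stake. One is some precision in the headache-day comparisons. The other is reproducibility: two programmers could fit different models and both claim to have followed the section. If the choice is left until treatment groups are known, it becomes a post hoc choice. The monthly and weekly headache models could also end up with different kinds of baseline.

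**Working it through.** **The plan's own figure.** The SAP's only power statement (section 5) is for the primary endpoint: 225 evaluable per arm, a 1-day difference, SD 3.75 days, two-sided alpha 0.05. The standard error is 3.75 × √(2/225) = 0.354. Then 1/0.354 = 2.83, 2.83 − 1.96 = 0.87, and Φ(0.87) gives about 80.7%, against the stated figure of roughly 80%. It reproduces and is not touched by this point, because the primary model has its matching covariate. The SAP gives no precision or power figure for headache days.

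**Reading the text.**

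| Model | Outcome switched? | Covariate switched in the text? |
|---|---|---|
| Moderate or severe migraine days per month (6.3.1.1) | yes | yes, numbered exception |
| Moderate or severe migraine days per week (6.3.3.3) | yes | yes, numbered exception |
| Total headache days per month (6.3.3.1) | yes | no |
| Moderate or severe headache days per month (6.3.3.1) | yes | no; all other variables said to be unchanged |
| Headache days per week (6.3.3.3) | yes | not stated; by analogy only |

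**Cost in precision.** The inputs are assumptions; neither document gives them.

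- R²: share of the variance in change explained by OP headache days, 0.15 to 0.35. With equal variances, R² = (1 − c)/2, where c is the correlation between baseline and later headache days, so this corresponds to c from 0.7 down to 0.3.
- r: correlation between OP headache days and OP migraine days, 0.70 to 0.95.
- OP migraine days carry no further information about the change once OP headache days are known.

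Scale the variance of the change to 1. Adjusting for the matching baseline leaves 1 − R². Under the third assumption the correlation of OP migraine days with the change is r × √R², so adjusting for migraine days leaves 1 − R²r². Hence

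SE ratio = √[(1 − R²r²)/(1 − R²)].

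| R² | r = 0.70 | r = 0.80 | r = 0.90 | r = 0.95 |
|---|---|---|---|---|
| 0.15 | 1.044 | 1.031 | 1.017 | 1.009 |
| 0.25 | 1.082 | 1.058 | 1.031 | 1.016 |
| 0.35 | 1.129 | 1.093 | 1.050 | 1.026 |

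Worked corners: √[(1 − 0.35 × 0.49)/0.65] = √(0.8285/0.65) = 1.129, and √[(1 − 0.15 × 0.9025)/0.85] = √(0.8646/0.85) = 1.009. The range is about 1% to 13%.

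**Imbalance.** Conditioning on OP migraine days accounts for r² of the variance in OP headache days: 0.70² = 0.49 to 0.95² = 0.90. About 10% to 51% is left unadjusted, so the correction is partial.

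**Simulation check.** With 225 per arm, one time point and 3,000 replicates, the mean treatment estimate under no effect was about 0 with either covariate. The variance ratio at c = 0.5 (R² = 0.25) was 1.08 for r = 0.9 and 1.19 for r = 0.7. The formula gives 1.06 and 1.17. This is a single-time-point approximation; the planned model has three months and robust standard errors.

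**The case against.** The best defence is the sentence on analogy near the start of 6.3.3.1. The natural analogue of change in migraine days adjusted for OP migraine days is change in headache days adjusted for OP headache days. The weekly headache-day text relies on analogy in the same way, and 6.3.3.4 uses the same except-for-the-outcome shorthand for acute migraine medication days. It is harmless there, because the model it borrows from 6.3.2.2 has no baseline covariate. All this fits drafting shorthand at least as well as a deliberate choice. It stands to this extent: a reader might infer that the sponsor has settled on the wrong baseline, and the documents do not show that. They show a general sentence and two specific sentences that disagree. The moderate or severe sentence, which fixes all other variables, is the hardest to reconcile with the analogy.

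A second objection is that the two baselines overlap heavily. SAP 9.2.5 notes: "Migraine days are a subset of headache days". That also stands. The correlation may well be high, which puts the total-headache model towards the low end of the range. It also rules out the inference that baseline imbalance is left wholly uncorrected.

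Third, a loss of precision is not a mathematical certainty. With equal variances, OP migraine days would be the better covariate if their correlation with headache days changed between baseline and follow-up by more than 1 − c. Ordinary assumptions point to a loss, but the documents do not establish one.

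The protocol supplied cannot decide the matter. It is for the acute-treatment study C4951022, while this SAP is for the prevention study C4951021.

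**Conclusion.** The point holds as an internal inconsistency with a probable, modest cost in efficiency. Taken at their word, the specific sentences in 6.3.3.1 adjust both headache-day outcomes for OP total migraine days. That contradicts the section's own analogy and the SAP's practice for migraine days. The standard error would be about 1% to 13% larger, and about 6% larger at R² = 0.25 and r = 0.8. These figures illustrate the three assumptions listed above and are not estimates for this trial. The mismatch is greatest in the moderate or severe model.

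A reader might go further and infer bias in the treatment effect. Randomisation rules that out: either covariate gives an unbiased estimate. Nor does anything here reach the trial's main conclusions. SAP 6.3.3 describes the headache-day endpoints as outside the formally listed exploratory objectives and their p-values as descriptive, and they are not in the testing hierarchy. This is a desirable clarification, not a required one.

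**What to change.** In SAP 6.3.3.1, state that the covariate is the number of headache days per month in the OP: total for the total model, moderate or severe for the moderate or severe model. In 6.3.3.3, state the per-week equivalent for the weekly headache-day models. Do this before treatment groups are unblinded at the primary completion database lock.

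The cost is one sentence in each section and one variable name in each program. No new derivation is needed, because SAP 6.2.5.2 already summarises OP headache days per month and per week, both total and moderate or severe.
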